5.7.4.1.4 Assessment of Causality

The investigator will assess the causal relationship/relatedness of each AE to the study drug using the following scale:

- Not Related: Onset of the AE has no reasonable temporal relationship to administration of the study drug, a causal relationship to administration of the study drug is biologically implausible, or the event is attributed to an alternative etiology.
- Unlikely Related: Onset of the AE has a reasonable temporal relationship to study drug administration and although a causal relationship is unlikely, it is biologically plausible.
- Possibly Related: Onset of the AE has a strong temporal relationship to administration of the study drug, cannot be explained by the subject's clinical state or other factors, and a causal relationship is biologically plausible.
- Probably Related: Onset of the AE shows a distinct temporal relationship to administration of the study drug that cannot be explained by the subject's clinical state or other factors, the AE is a known reaction to the product or chemical group, or can be predicted by the product's pharmacology.

5.7.4.1.5 Pregnancy

A serum pregnancy test will be performed for female subjects at the time points presented in the Schedules of Events (Table 9-1). If a subject becomes pregnant while on the study,

this should be reported immediately to the investigator, the subject will be withdrawn from the study and the medical monitor and the subject will be instructed to follow-up with his or her personal physician. All pregnancies are to be reported as an AE and followed for outcome.

5.7.4.2 Clinical Laboratory Tests

Clinical laboratory and diagnostic screening tests will be performed at the time points presented in the Schedules of Events (Table 9-1) and will be collected in accordance with acceptable laboratory procedures. Clinical laboratory testing will be performed by the clinical study contractor. The clinical laboratory tests that will be performed are presented in Table 5-2. Unused clinical laboratory test samples will not be stored for future use.

Table 5-2: Clinical Laboratory Tests and Diagnostic Screening Tests

Hematology	Serum Chemistry	Urinalysis
Hematocrit Hemoglobin Platelet count Red blood cell count White blood cell count (with automated differential)	Alanine aminotransferase Albumin Alkaline phosphatase Aspartate aminotransferase Bicarbonate Bilirubin (total, direct, and indirect) Blood urea nitrogen Calcium Chloride Creatinine (including calculated creatinine clearance) Glucose Lactate dehydrogenase Magnesium Phosphorus Potassium Sodium Total protein Uric acid	Appearance Bilirubin Blood Color Glucose Ketones Leukocyte esterase Microscopic examination: red blood cells, white blood cells, epithelial cells, bacteria, crystals, and casts (if present) Nitrite pH Protein Specific gravity Urobilinogen
Diagnostic Screening Tests:		
Serum Serology (human immunodeficiency virus Ag/Ab Combo 1/2, hepatitis C virus antibody, and hepatitis B surface antigen) Female Subjects Only Human chorionic gonadotropin (for pregnancy)	Urine Drug screen including: amphetamines, barbiturates, benzodiazepines, cannabinoids, cocaine, alcohol, opiates, phencyclidine, propoxyphene, and methadone	Other SARS-CoV-2 molecular test

Clinical laboratory results will be reviewed by the investigator or designee together with data in the eCRF. Any values outside the reference range will be evaluated for clinical significance. If a value is determined to be clinically significant, the subject will be instructed to follow-up with his or her personal physician. The investigator or designee may repeat the clinical laboratory tests if deemed appropriate. The investigator will maintain a copy of the laboratory accreditation and the reference ranges for the laboratory used.

5.7.4.3 Vital Sign Measurements

Vital signs (blood pressure, heart rate, respiratory rate, and oral body temperature) will be measured using an automated device at the time points presented in the Schedules of Events (Table 9-1). The subject should be in a supine position, if possible, for a minimum of 5 minutes before vital signs are measured.

5.7.4.4 Safety 12-lead Electrocardiograms

12-lead ECGs will be obtained with the subjects in the supine position for a minimum of 5 minutes before recording. ECGs will be overread by a physician. If an abnormality is observed, the subject will be instructed to follow-up with his or her personal physician.

5.7.4.5 Physical Examinations

A complete physical examination will be performed at the time points presented in the Schedules of Events (Table 9-1).

The complete physical examination will include, but not be limited to, assessments of the head, eyes, ears, nose, throat, skin, thyroid, nervous system, respiratory system, cardiovascular system, abdomen (liver and spleen), lymph nodes, and extremities. Height, weight (without shoes and wearing the lightest possible clothing), and calculation of body mass index will be performed at Screening and Study Termination only.

If a clinically significant abnormality is observed upon physical examination, the subject will be instructed to follow-up with his or her personal physician.

5.7.5 Demographics and Medical History

Demographic data (date of birth, gender, race, and ethnicity) will be collected at Screening.

Each subject will provide a complete medical history at Screening that will be reviewed at Check-in. Specific information relating to any prior or existing medical conditions/surgical procedures will be recorded in the subject's eCRF.

5.8. Study Treatments

For each of the study drugs, doses were selected based on the doses studied in prior PD and PK studies.

5.8.1 Treatments Administered

On Day 1, subjects will receive 1 of the following 9 treatments according to the randomization schedule:

- Treatment Group A: Mepolizumab 3 mg, SC
- Treatment Group B: Mepolizumab 6 mg, SC
- Treatment Group C: Mepolizumab 12 mg, SC
- Treatment Group D: Mepolizumab 24 mg, SC
- Treatment Group E: Reslizumab 0.1 mg/kg, IV
- Treatment Group F: Reslizumab 0.2 mg/kg, IV

- Treatment Group G: Reslizumab 0.4 mg/kg, IV
- Treatment Group H: Reslizumab 0.8 mg/kg, IV
- Treatment Group I: Placebo, (4 subjects receive SC and 4 subjects receive IV)

Study drugs will be administered by a clinical research nurse on the study clinic floor at the subject's bedside. The pharmacist and investigator will be available if needed during study drug administration.

Note: Reslizumab must be given as an intravenous infusion only. Do not administer as an intravenous push or bolus.

5.8.2 Dose Selection

5.8.2.1 Mepolizumab

The doses selected for mepolizumab are 3 mg, 6 mg, 12 mg, and 24 mg single dose SC injection. The dose selection rationale is based on both the PK and PD dynamic range of mepolizumab.

This dose range will also cover the sensitivity of dose-area-under-the effect curve (AUEC) relationship and dose- E_{max} (nadir) relationship of the PD response (blood eosinophils). As the primary goal is to characterize the PD profiles of blood eosinophils following low, intermediate low, intermediate high, and high dose of mepolizumab, 3 – 24 mg single dose will be administered. Doses within the study range and greater have been safely administered to healthy subjects.

5.8.2.2 Reslizumab

The doses selected for reslizumab are 0.1 mg/kg, 0.2 mg/kg, 0.4 mg/kg, and 0.8 mg/kg single dose IV infusion. The dose selection rationale is based on both the PK and PD dynamic range of reslizumab.

This dose range will also cover the sensitivity of dose-area-under-the effect curve (AUEC) relationship and dose- E_{max} (nadir) relationship of the PD response (blood eosinophils). As the primary goal is to characterize the PD profiles of blood eosinophils following a range of doses of reslizumab that do not saturated the biological response, 0.1 – 0.8 mg/kg single dose will be administered. Doses within the study range and greater have been safely administered to healthy subjects.

5.8.3 Method of Assigning Subjects to Treatment Sequence

5.8.3.1 Randomization Process

The project biostatistician will create the specifications that will be used to generate the randomization schedule. The specifications will be based on the protocol requirements and appropriate statistical programming with consideration for study design, number of treatments, number of subjects planned for enrollment, stratification, and blocking.

Based on these specifications, the project biostatistician (or designee) will generate a dummy randomization schedule. The schedule is generated using R.

The project biostatistician (or designee) distributes the ‘dummy’ randomization schedule to specified personnel for review. Any change (e.g., change in block size, change in stratification levels) that requires an update to the specifications will reset this process. Minor changes (e.g., display formatting) will not require a change to the specifications.

After the approval of the ‘dummy’ randomization schedule, the project biostatistician (or designee) transfers the program used to generate the ‘dummy’ schedule to the randomization biostatistician (unblinded), who is an independent party and will not be participating in any programming or statistical decisions for the study before breaking the blind. No transfer is necessary if the unblinded randomization biostatistician also created the ‘dummy’ randomization.

The randomization biostatistician is responsible for generating the final randomization schedule. The output is sent only to designated unblinded recipients, who will maintain a secured digital and printed copy for their use.

Archival of the programs and output is accomplished by the creation of an encrypted, password-protected ZIP file containing the program and output file(s). The ZIP file is copied to a secure storage drive at the sponsor’s site.

Randomization will occur after informed consent is obtained, either after completion of check-in procedures on Day -1 or just before dosing on Day 1. Approximately 72 healthy male and female subjects are planned for enrollment. Up to 14 subjects may be qualified as replacements as described in Section 5.5.2. Thus, a maximum of 86 subjects will be exposed to study drugs and procedures during the study. Unique subject numbers will be used in sequential order based on each subject’s order of qualification.

Enrolled subjects will be randomly assigned to 1 of 9 different treatment groups. The treatment groups are presented in Table 5-3.

Table 5-3: Study Treatment Groups

Subjects (n)	Treatment Group	Drug
8	A	Mepolizumab low (3 mg)
8	B	Mepolizumab low intermediate (6 mg)
8	C	Mepolizumab high intermediate (12 mg)
8	D	Mepolizumab high (24 mg)
8	E	Reslizumab low (0.1 mg/kg)
8	F	Reslizumab low intermediate (0.2 mg/kg)
8	G	Reslizumab high intermediate (0.4 mg/kg)
8	H	Reslizumab high (0.8 mg/kg)
8	I	Placebo

All randomization information will be secured and housed in a locked storage area, accessible only by the randomization personnel and the assigned pharmacist and his or her verifier.

5.8.4 Identity of Study Drugs

Mepolizumab (NUCALA) is an interleukin-5 (IL-5) antagonist monoclonal antibody indicated for add-on maintenance treatment of patients with severe asthma with an eosinophilic phenotype, aged 12 years and older. It is produced by recombinant DNA technology in Chinese hamster ovary (CHO) cells. Mepolizumab has a molecular weight of approximately 149 kg/ mol (149 kDa). It is supplied as a sterile, lyophilized powder; upon reconstitution with 1.2 mL sterile water, the resulting concentration is 100 mg/ mL and delivers 1 mL for single-dose use.

Reslizumab (CINQAIR) is an IL-5 antagonist monoclonal antibody indicated for add-on maintenance therapy of adult patients with severe asthma, with an eosinophilic phenotype. It is produced by recombinant DNA technology in murine myeloma non-secreting 0 (NS0) cells. Reslizumab has a molecular weight of approximately 147 kg/ mol (147 kDa) and it's available as a 100 mg/ 10 mL (10 mg/ mL) solution in single-use vials.

Subjects administered placebo will received either a placebo subcutaneous injection or placebo IV infusion. A placebo subcutaneous injection of equal volume and comparable pH to the diluent for high dose mepolizumab will be injected into upper arm subcutaneously for 4 subjects in the placebo treatment arm. A placebo IV infusion of equal volume and comparable pH to the diluent for reslizumab will be administered to 4 subjects in the placebo treatment arm.

5.8.5 Management of Clinical Supplies

5.8.5.1 Study Drug Packaging and Storage

The active study drugs will be obtained from commercial sources. Storage instructions for the active study drugs are as follows:

- Mepolizumab should be stored below 25 °C (77 °F). Do not freeze. Vials should be protected from the light by storing in the original package until time of use. If reconstituted mepolizumab is not used immediately, it should be stored below 30 °C (86 °F), not frozen, and discarded if not used within 8 hours of reconstitution.
- Reslizumab should be stored at 2 °C – 8 °C (36 °F – 46 °F). Do not freeze. Do not shake. Vials should be protected from the light by storing in the original package until time of use.
- Placebo should be stored below 25 °C (77 °F). Do not freeze. Vials should be protected from the light until time of use.

5.8.5.2 Study Drug Accountability

Good clinical documentation practices will be employed to record the receipt, storage conditions, accountability, and use or return of the study drug. The study drug will be stored in a secure location with access to the study personnel who will be managing the storage, dispensing, and accountability of the study drug.

Upon completion or termination of the study, final accountability review by the study monitor, and written authorization from the FDA, all unused and/or partially used study drug should be returned or destroyed at the study clinic. It is the investigator's responsibility to ensure that the sponsor has provided written authorization for study drug disposal, the disposal process follows the study clinic's standard operating procedures, and appropriate records of the disposal are documented and maintained. No unused study drug may be disposed until fully accounted for by the study monitor (or designee). Documentation of unused study drug should include subject number, medication identity (medication #, period #), date, and quantity of study drug used.

5.8.6 Blinding

The pharmacist (and designated staff member responsible for confirmation of study drug dose) will be unblinded to subject treatment assignment; however, the pharmacist will not perform any study procedures other than study drug preparation and dispensing.

Subjects and staff will be blinded to treatment assignment during confinement, but route of administration will not be blinded. The blind will be maintained through a randomization schedule held by the dispensing pharmacist. Subjects and staff will be informed of a subject's end of study day when discharged from confinement. Subjects and staff will not be informed of the specific treatment arm assignment. The clinical research nurse will administer the study drugs in unit dose containers that are not transparent.

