2. Parameters (E_{max} , and EC_{50}) calculated by the model after combining data from low, intermediate low, intermediate high, and high doses of mepolizumab or reslizumab with placebo data.

Exploratory Endpoints

1. Plasma proteomics (differential expression of circulating proteins)

2. Plasma small RNA transcriptomics (differential expression of circulating small RNAs)

Study Design:

This is a pilot, randomized, placebo-controlled, single-dose, parallel arm study. Healthy subjects will be randomized to four dose groups (low, intermediate low, intermediate high, and high) of each drug (mepolizumab or reslizumab) or placebo.

Subjects will report to the study site for screening assessments from Days -21 to -2 and then will return to the site on Day -1 for baseline assessments. Prior to and following study drug or placebo administration on Day 1, they will undergo assessments as described in the Schedule of Events (Table 9-1). Subjects will stay in house for the first two weeks.

Depending on the treatment arm, subjects will return to the clinic a maximum of 9 times for PK and PD blood draws and additional study procedures as outlined in the Schedule of Events.

Subjects will be sampled daily for the first two weeks, weekly out to day 63 and half of the dosed subjects will be sampled monthly until day 123. Each treatment group should include equal representation of male and female subjects. For all scheduled outpatient visits (i.e., all visits after 2 weeks of in house residency, see Table 9-1), subjects will be required to return to the clinic within a four-hour window.

The planned cohort sizes and investigational product doses are as follows:

Subjects (n)	Treatment Group	Drug
8	A	Mepolizumab low (3 mg)
8	B	Mepolizumab low intermediate (6 mg)
8	C	Mepolizumab high intermediate (12 mg)
8	D	Mepolizumab high (24 mg)
8	E	Reslizumab low (0.1 mg/kg)
8	F	Reslizumab low intermediate (0.2 mg/kg)
8	G	Reslizumab high intermediate (0.4 mg/kg)
8	H	Reslizumab high (0.8 mg/kg)
8	I	Placebo

Subjects in groups A, B, E, and F will follow the Schedule of Events through day 63. Subjects in groups C, D, G, and H and placebos will follow the Schedule of Events through Day 123.

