5.1. Study Design

This is a pilot, randomized, placebo-controlled, single-dose, parallel arm study. Healthy subjects will be randomized to four dose groups (low, intermediate low, intermediate high, and high) of each drug (mepolizumab or reslizumab) or placebo (see Table 5-1).

Subjects will report to the study site for screening assessments from days -21 to -2 and then will return to the site on day -1 for baseline assessments. Prior to and following

study drug or placebo administration on day 1, they will undergo assessments as described in the Schedule of Events (Table 9-1). Subjects will stay in house for the first two weeks and will return to the clinic for study procedures as identified in the Schedule of Events (Table 9-1).

Depending on the treatment arm, subjects will return to the clinic up to 9 times for PK and PD blood draws and additional study procedures as outlined in the Schedule of Events (Table 9-1).

All subjects will be sampled daily for the first two weeks and then weekly out to Day 63. Subjects in Groups C, D, G, H, and I will be sampled monthly until Study Day 123. Subjects in Groups A, B, E, and F will follow the Schedule of Events until Day 63 and all other subjects will follow the Schedule of Events until Day 123. Each treatment group should include equal representation of male and female subjects.

Table 5-1: Study Treatment Groups

Subjects (n)	Treatment Group	Drug
8	A	Mepolizumab low (3 mg)
8	B	Mepolizumab low intermediate (6 mg)
8	C	Mepolizumab high intermediate (12 mg)
8	D	Mepolizumab high (24 mg)
8	E	Reslizumab low (0.1 mg/kg)
8	F	Reslizumab low intermediate (0.2 mg/kg)
8	G	Reslizumab high intermediate (0.4 mg/kg)
8	H	Reslizumab high (0.8 mg/kg)
8	I	Placebo

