5.1.2 Dosing Schedule

- Treatment Group A: Mepolizumab 3 mg, SC
- Treatment Group B: Mepolizumab 6 mg, SC
- Treatment Group C: Mepolizumab 12 mg, SC
- Treatment Group D: Mepolizumab 24 mg, SC
- Treatment Group E: Reslizumab 0.1 mg/kg, IV
- Treatment Group F: Reslizumab 0.2 mg/kg, IV
- Treatment Group G: Reslizumab 0.4 mg/kg, IV
- Treatment Group H: Reslizumab 0.8 mg/kg, IV
- Treatment Group I: Placebo, (4 subjects receive SC and 4 subjects receive IV)

Subjects in Groups A, B, E, and F will be discharged on Day 63, while all other subjects will be discharged on Day 123. If a subject discontinues from the study prematurely, all procedures scheduled for discharge Day (i.e., Day 63 or Day 123) will be performed.

Meal timing and components, activity levels, and general conditions in the study clinic will be as similar as possible on the treatment days.

Safety will be evaluated in terms of AEs, clinical laboratory results (hematology, serum chemistry, and urinalysis), vital sign measurements (blood pressure, heart rate, respiratory rate, and oral body temperature), safety 12-lead ECG results, and physical examination findings (see Table 9-1).

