5.2. Selection of Study Population

Subjects will be screened, and the data collected will be reviewed by the principal investigator. Only those subjects who meet all the eligibility criteria will be enrolled. Approximately 72 healthy subjects are planned for enrollment. Up to 14 subjects may be qualified as replacements as described in Section 5.5.2. Thus, a maximum of 86 subjects will be exposed to study drugs and procedures during the study. Every effort will be made to maintain an approximate 50:50 male to female sex distribution.

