3.1. Study design

This is a randomized, double-blind, placebo-controlled, single-dose, parallel arm, pilot study. Healthy subjects will be randomized to one of four dose groups (low, intermediate low, intermediate high, and high) of each drug (mepolizumab and reslizumab) or placebo (Table 1). The study will be conducted at one center in the United States (Spaulding Clinical Research unit in West Bend, Wisconsin).

Subjects will report to the study site for screening assessments from days -21 to -2 and then will return to the site on day -1 for baseline assessments. Prior to and following study drug or placebo administration on day 0, they will undergo assessments as described in the Schedule of Events. Subjects will stay in house for the first two weeks and will return to the clinic for study procedures as identified in the Schedule of Events Depending on the treatment arm, subjects will return to the clinic up to 9 times for PK and PD blood draws and additional study procedures as outlined in the Schedule of Events.

All subjects will be sampled daily for the first two weeks and then weekly out to Day 63. Subjects in Groups C, D, G, H, and I will be sampled monthly until Study Day 123. Subjects in Groups A, B, E, and F will follow the Schedule of Events until Day 63 and all other subjects will follow the Schedule of Events until Day 123. Each treatment group should include equal representation of male and female subjects.

Table 1: Study Treatment Groups

Statistical Analysis Plan: SCR-006

Subjects (n)	Treatment Group	Drug
8	A	Mepolizumab low (3 mg)
8	В	Mepolizumab low intermediate (6 mg)
8	С	Mepolizumab high intermediate (12 mg)
8	D	Mepolizumab high (24 mg)
8	Е	Reslizumab low (0.1 mg/kg)
8	F	Reslizumab low intermediate (0.2 mg/kg)
8	G	Reslizumab high intermediate (0.4 mg/kg)
8	Н	Reslizumab high (0.8 mg/kg)
8	I	Placebo

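### Disclosing the end-of-study day at about Day 14 lets staff identify 32 of 72 subjects as on active drug, so the unqualified double-blind label in SAP 3.1 is wrong

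*Protocol*

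**What the plan says.** Protocol 5.8.6 limits the treatment blind for subjects and staff to the confinement period and adds that "route of administration will not be blinded". It then says that both will be told a subject's "end of study day when discharged from confinement", and that neither will be told the specific arm. Confinement is the first two weeks (Protocol 5.1).

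The end day depends on the group. Protocol 5.1.2 states: "Subjects in Groups A, B, E, and F will be discharged on Day 63, while all other subjects will be discharged on Day 123". The synopsis puts placebo in the longer schedule: "Subjects in groups C, D, G, and H and placebos will follow the Schedule of Events through Day 123". Mepolizumab is given SC and reslizumab IV, and placebo is split 4 SC and 4 IV (Protocol 5.1.2).

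The design statements in the protocol (synopsis, 5.1 and 5.6.3) do not use the term double-blind. SAP 3.1 does: "This is a randomized, double-blind, placebo-controlled, single-dose, parallel arm, pilot study". The same SAP section repeats the Day 63 and Day 123 split.

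**The concern.** The end-of-study day carries treatment information because no placebo subject has the short schedule. Together with the open route, a Day 63 end date shows that the subject is on active drug, which drug it is, and that the dose is one of that drug's two lower levels. No randomization list is needed.

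What is at stake is judgement-based data collected after disclosure. AEs are recorded until discharge (Protocol 5.7.4.1.2), and the investigator rates their severity and causality (5.7.4.1.3 and 5.7.4.1.4). Treatment-emergent events are then summarised by severity, relationship and treatment (Protocol 5.9.8.1, SAP 7.7.1). For the Day 63 groups, ratings after about Day 14 would be made with active treatment inferable, while for the higher-dose and placebo groups some doubt remains. A report that takes its design description from SAP 3.1 would claim a property that the trial does not have over this period.

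**Working it through.** **Inputs.** There are nine groups of 8 (Protocol Table 5-1). The planned total is given as "Approximately 72 healthy subjects are planned for enrollment" and, for replacements, "Up to 14 subjects may be qualified as replacements" (Protocol 5.2). Confinement of two weeks puts disclosure at about Day 14.

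**The plan's own total.** 9 × 8 = 72, and 72 + 14 = 86. Both agree with Protocol 5.2. Protocol 5.9.1 speaks of nine active arms plus 8 placebo subjects, which would give 9 × 8 + 8 = 80. The group tables and SAP 3.2 give eight active arms plus placebo, so 72 is used here.

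**Cross-classification by what staff know after discharge from confinement.**

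| Route | End day | Groups | Subjects | Placebo | P(active) |
|---|---|---|---|---|---|
| SC | 63 | A, B | 16 | 0 | 16/16 = 100% |
| SC | 123 | C, D, half of I | 20 | 4 | 16/20 = 80% |
| IV | 63 | E, F | 16 | 0 | 16/16 = 100% |
| IV | 123 | G, H, half of I | 20 | 4 | 16/20 = 80% |

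**Before disclosure.** Within each route, P(active) = 32/36 = 89%. Overall it is 64/72 = 89%.

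**After disclosure.**
- Identifiable as active: 4 × 8 = 32 subjects. That is 32/72 = 44% of all subjects and 32/64 = 50% of active subjects.
- Of these 32, 16 are at the low level (A, E) and 16 at low intermediate (B, F). The end day does not separate the two.
- For the other 40, P(placebo) rises from 4/36 = 11% to 4/20 = 20% within each route.

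**Duration.** In the Day 63 groups, 63 − 14 = 49 of 63 days (78%) follow disclosure. They contain seven scheduled visits: Days 21, 28, 35, 42, 49, 56 and 63.

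**Replacements.** A replacement takes the treatment of the subject replaced (Protocol 5.5.2). If all 14 are used and none falls in A, B, E or F, the share is 32/86 = 37%. If all 14 do, it is 46/86 = 53%.

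**If the end day is held until the Day 63 visit.** The sampling calendar is common to all groups up to that day, so 0 of 72 subjects are identifiable from the end day between Day 14 and Day 63. P(placebo) stays at 4/36 = 11% within each route until then.

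**The case against.** The strongest reply is that the protocol hides nothing. Section 5.8.6 states the open route, the scope of the blind and the time of disclosure, and the protocol never claims to be double-blind. On that view the only textual error is one term in SAP 3.1. This stands as far as it goes: the label is the error, and the timing of disclosure is an avoidable design choice.

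The change in knowledge is also modest. With 8:1 allocation, every subject was already 89% likely to be on active drug. That is correct, and it is why the shift should be given as 89% to 100% and 89% to 80%, alongside the count of 32.

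A reader might infer four stronger things that the documents do not support:
- **That the 32 are known to be on the low dose.** Half are at low intermediate, and 5.8.6 keeps the specific arm undisclosed.
- **That subjects know they are on active drug.** They would need to know which groups end on Day 63. The consent pages were removed from the text reviewed, so this cannot be checked. For staff, who have the protocol, the inference is sound.
- **That the primary results are biased.** Eosinophils are counted by flow cytometry on samples sent to an outside laboratory (Protocol 5.7.2.2.1), and drug concentrations are assayed at FDA. An indirect route through dropout exists, since SAP section 5 excludes early terminators from PK and PD summaries, but nothing in the documents lets its size be estimated.
- **That a safety comparison fails.** Safety is not among the listed objectives or endpoints, the AE tables are descriptive, and the first two weeks after the single dose precede disclosure.

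Finally, withholding the end day would not by itself secure the blind. The investigator or designee reviews hematology that includes an automated white-cell differential (Protocol 5.7.4.2, Table 5-2), which may show eosinophil suppression. This limits what the fix can achieve but does not justify the label.

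**Conclusion.** The point holds. From about Day 14, staff can identify 32 of 72 planned subjects (44%) as receiving active treatment with a known drug at one of its two lower dose levels. Their probability of active treatment moves from 89% to 100%, and that of the other 40 from 89% to 80%. Dose level within each end-day set remains masked, as does active versus placebo in the Day 123 set, so the blind is weakened rather than lost.

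The unqualified term in SAP 3.1 does not describe this design. The practical exposure is mainly AE severity and causality ratings after Day 14, which enter descriptive tables; the laboratory-based PK and PD endpoints should be little affected.

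This rests on planned group sizes, disclosure at about Day 14, and staff knowing the group schedules from the protocol. The size of any effect on AE ratings cannot be derived from the documents.

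**What to change.** 1. **SAP 3.1.** Replace the double-blind label with wording that matches Protocol 5.8.6: blinded to dose level and to active versus placebo within an open route, with active status inferable for the Day 63 groups once the end day is disclosed.
2. **Protocol 5.8.6.** Have an unblinded role, such as the pharmacist, hold the end-of-study day until the Day 63 visit. Disclose it after that visit's AE query and AE ratings are recorded and before the discharge-only procedures of Protocol 5.6.4.

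The cost is wording in both documents and a fixed order of events at the Day 63 visit. Subjects would learn later whether Days 93 and 123 apply to them, and with that when restrictions tied to study duration end. An event first found in the Day 63 discharge procedures would still be rated after disclosure. After Day 63 the continuing schedule itself shows that a subject is not in A, B, E or F.

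If early disclosure is kept for scheduling, change 1 is still needed, with a note that AE ratings after Day 14 were made with active status inferable for these 32 subjects.
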